4.3. Randomization Criteria

This will be a single-arm, non-randomized study.

4.4. Lifestyle Guidelines

All subjects in this study will be women, aged 18-45, who are willing to use Sayana Press at home. Study subjects will self-inject Sayana Press at home according to study schedule (13 week interval +/- 1 week). If the subject fails to self-inject or report to clinic for an injection (supervised or administered by HCP) within this +/- 1 week treatment window, she should be advised to use a barrier method of contraception as instructed by the study investigator until she administers the next injection or, in cases when the subject decides to discontinue Sayana Press altogether, until the new contraceptive regimen is established. A pregnancy test should also be conducted prior to the next scheduled injection.

4.5. Investigator Approval for Self-Injection

Subjects who meet all inclusion criteria and none of the exclusion criteria will undergo training in self-injection at the Baseline Visit which will culminate in the subject attempting to perform the first self-injection of Sayana Press under the supervision of the investigator (or suitable designee). At this point, the investigator will approve (or not approve) the subject to go forward in the study and be permitted to attempt the 3 subsequent self-injections at home, based on the investigator's assessment of the subject's proficiency at self-injection. Subjects who are not approved for self-injection at this point will be discontinued from the study.

4.6. Sponsor's Qualified Medical Personnel

The contact information for the sponsor's appropriately qualified medical personnel for the study is documented in the study contact list located in the supporting study documentation.

To facilitate access to appropriately qualified medical personnel on study-related medical questions or problems, subjects are provided with a contact card. The contact card contains, at a minimum, protocol and investigational compound identifiers, subject study numbers, contact information for the investigational centre, and contact details for a contact centre in the event that the investigational centre staff cannot be reached to provide advice on a medical question or problem originating from another healthcare professional not involved in the subject's participation in the study. The contact number can also be used by investigational staff if they are seeking advice on medical questions or problems; however, it should be used only in the event that the established communication pathways between the investigational centre and the study team are not available. It is therefore intended to augment, but not replace, the established communication pathways between the investigational centre and the study team for advice on medical questions or problems that may arise during the study. The contact number is not intended for use by the subject directly, and if a subject calls that number, he or she will be directed back to the investigational centre.

5. STUDY INTERVENTION

For the purposes of this study, and per International Conference on Harmonization (ICH) guidelines study drug is defined as a pharmaceutical form of an active ingredient or placebo being tested or used as a reference in a clinical trial, including a product with a marketing authorization when used or assembled (formulated or packaged) in a way different from the approved form, or when used for an unapproved indication, or when used to gain further information about an approved use (ICH E6 1.33). Study drug in this study will be the currently marketed, commercial Sayana Press.

5.1. Allocation to Treatment

This is a non-randomized single arm study and all study subjects will be receiving the same treatment.

5.2. Subject Compliance

To document compliance, study participants will be asked to contact the clinic by phone after performing each scheduled self-injection in order to confirm the date of injection. If at least 1 week has passed from the scheduled self-injection date and the clinic has not heard from the subject, the clinic staff will contact the subject to obtain the necessary information and provide appropriate instructions to the subject, depending on the circumstances.

The investigator will provide training to the study subjects regarding the safe and correct use of Sayana Press according to standard of care, using currently available training materials that will include tools designed to facilitate the training of subjects in self-injection and that assist subjects in remembering the scheduled injection dates. Since this study is intended to be relevant to clinical practice, and with respect to materials intended to remind study subjects of the proper injection date (reminder materials), Investigators should use reminder materials and techniques that may be employed in their practice for patients using 3-monthly DMPA (eg, an appointment card or reminder phone call or other electronic methods for reaching out to patients to encourage compliance with the standard DMPA 3-monthly visit schedule).

5.3. Study Drug Supplies

5.3.1. Dosage Form(s) and Packaging

Sayana[®] Press delivery system is commercially available. The sponsor will centrally supply this product to be used in accordance with local regulations and according to the commercial usage instructions.

5.3.2. Preparation and Dispensing

See the included commercial package leaflet for instructions on how subjects will administer the study drug. Each unit will be individually packaged in single-use foil pouches. The pouches should not be opened until the study drug is to be administered. Each subject will receive enough product units to cover the required number of doses for the length of the study.

5.3.3. Administration

The product will be administered in accordance with the label.

Study participants will be taught how to self-administer Sayana Press by the investigator or study centre staff using the training materials used according to standard of care in their practice, which are based on the approved Instructions for Use (IFU) for Sayana Press (Appendix 2). If the subject is comfortable attempting the Baseline Visit self-injection, the first self-injection will be performed at the clinic under the supervision of the study centre staff. If the subject adequately performs the first self-injection, and the investigator approves the subject to continue in the study, based on the subject's proficiency exhibited during the first self-injection, the subject will be then provided with 3 Sayana Press delivery system packages to take home. Subjects will be also given a copy of the Sayana Press IFU and contact information for the clinic. Subjects may also be given a reminder card or other reminder tools at the discretion of the Investigator.

If a self-injection did not occur due to malfunction or damage to the Sayana Press injector, a replacement Sayana Press injector should be provided to the subject at an unscheduled visit to replace it and the subject should self-inject immediately upon returning home.

If a scheduled injection is been delayed beyond the protocol-specified window (scheduled injection date ± 1 week), the subject should be advised to contact the clinic and speak to a healthcare professional regarding the need to exclude pregnancy before any additional injections, advice regarding additional contraception, and also for the timing of the next injection. A pregnancy test should also be conducted prior to the next scheduled injection.

Details regarding subject self-injection issues and reasons for self-injection failure must be documented in the subject's primary source records.

Following self-injection, the used Sayana Press injector should be immediately disposed of into a suitable container in accordance with the local regulatory authority requirements or per instructions from the Investigator.

5.4. Study Drug Storage

The investigator, or an approved representative, eg, pharmacist, will ensure that all study drugs are stored in a secured area with controlled access under required storage conditions and in accordance with applicable regulatory requirements.

Study Drug should be stored in its original container and in accordance with the label. See the Summary of Product Characteristics for storage conditions of the product. Storage conditions stated in the SRSD will be superseded by the storage conditions stated in the labeling.

Centre systems must be capable of measuring and documenting (for example, via a log), at a minimum, daily minimum and maximum temperatures for all centre storage locations (as applicable, including frozen, refrigerated and/or room temperature products). This should be captured from the time of investigational product receipt throughout the study on all business days. Even for continuous monitoring systems, a log or centre procedure that ensures active daily evaluation for excursions should be available. The operation of the temperature monitoring device and storage unit (for example, refrigerator), as applicable, should be regularly inspected to ensure it is maintained in working order.

Any excursions from the product label storage conditions should be reported upon discovery. The centre should actively pursue options for returning the product to the storage conditions, as soon as possible. Deviations from the storage requirements, including any actions taken, must be documented and reported to the sponsor. Once an excursion is identified, the study drug must be quarantined and not used until the sponsor provides documentation of permission to use the investigational product. It will not be considered a protocol deviation if the sponsor approves the use of the study drug after the temperature excursion. Use of the investigational product prior to sponsor approval will be considered a protocol deviation.

Specific details regarding information the centre should report for each excursion will be provided to the centre.

Centre staff will instruct subjects on the proper storage requirements for take home study drugs including how to report temperature excursions. In the event of any significant temperature changes (eg, left study drug in a hot car for several hours) after the subject takes the study drug home from the study centre, the subject is not to use this study drug and should contact the study centre immediately to return that study drug and obtain a replacement supply. The study centre will quarantine any study drug that was returned by a subject due to significant temperature changes and not redispense it.

5.5. Study Drug Accountability

The investigative centre must maintain adequate records documenting the receipt, use, loss, or other disposition of the study drug supplies. All unused study drug product will be returned to the investigator by the subject upon completion of the study or discontinuation.

5.6. Destruction of Study Drug Supplies

The sponsor or designee will provide guidance on the destruction of unused study drug (eg, at the centre). If destruction is authorized to take place at the study centre, the investigator must ensure that the materials are destroyed in compliance with applicable environmental regulations, institutional policy, and any special instructions provided by Pfizer, and all destruction must be adequately documented.

5.7. Concomitant Treatment(s)

Medications that are contraindicated with Sayana Press (as per current prescribing information) will be prohibited.

6. STUDY PROCEDURES

6.1. Screening (Days -14 to 1)

Screening visit may take place on the same day as Baseline Visit or on a different day (within 14 days prior to Baseline Visit).

The investigator (or an appropriate designee) will obtain written informed consent from each participant in accordance with the approved ICD. Participants will be screened prior to enrollment to confirm that they meet the enrollment criteria for the study. The following screening procedures will be performed:

- Written, informed consent obtained prior to performance of any testing, examination or treatment;
- Medical history;
- Demographics
- AE assessment;
- Prior medications;
- Physical examination;
- Vital signs (sitting blood pressure and heart rate);
- Urine pregnancy test.

6.2. Study Period Baseline Visit (Day 1)

Baseline Visit may take place on the same day as Screening Visit or on different days.

Following procedures will be performed at this visit:

- Registration in the study;
- AE assessment;
- Vital signs (sitting blood pressure and heart rate);
- Height and Weight;
- Prior medications for the 2-week period prior to Baseline Visit;
- Urine pregnancy test;
- Record subject's educational level;
- Self-injection training including first self-injection;

The baseline training and patient-directed training materials given to study participants will be those used according to standard of care for patients in their practice.

The training materials should include suggested methods for remembering the scheduled injection dates per standard of care. Investigators may also utilize patient reminder techniques in this study that align closely with techniques they normally use in their practice for women receiving DMPA injections every 3 months in the clinic (eg, an appointment card, phone call, text message or other electronic methods for reaching out to patients to encourage compliance with the standard DMPA 3-monthly visit schedule). However, under this protocol investigators are not required to utilize any such outreach method to encourage compliance. Because training techniques, training materials and reminder techniques might differ from centre to centre, such methods and the way they were delivered will be documented for each centre;

- Injection difficulties or any problems with the device will be recorded in the CRF;
- Investigator approval of self-injection proficiency;

Three packages containing Sayana Press delivery system will be distributed to each study subject for home self-injection.

Months 3, 6 and 9 (subject phone assessment)

Study subjects will self-inject Sayana Press at home according to schedule (13 week interval +/- 1 week). They will be asked to contact the clinic by phone after performing each self-injection in order to confirm the date on which the injection was performed and report any AEs, including unplanned pregnancy, concomitant medications and injection site reactions. During this phone call, the clinic staff will also record whether the subject had any difficulties in performing the injection or had problems operating the device and what those issues were. In case the subject reports any injection site reactions, clinic staff will collect detailed information about the reaction (eg, timing; persistence; appearance; is it getting worse or better; how large or deep is it; how bothersome, etc.). All AEs, including unplanned pregnancy and injection site reactions will be recorded on AE CRF page. Reasons for self-injection failure will also be recorded in the CRF.

If a participant fails to contact the clinic to report the injection date, the study centre personnel shall not contact the patient until after the treatment window (+/- 1 week) for that planned injection has expired. If at least 1 week has passed from the scheduled self-injection date and the clinic has not heard from the subject, the clinic staff will contact the subject to obtain the necessary follow-up information and provide appropriate instructions to the subject, depending on the circumstances.

If the subject fails to self-inject or report to clinic for an injection (supervised or administered by HCP) within the +/- 1 week treatment window, the subject should be advised to contact the clinic and speak to a healthcare professional regarding the need to exclude pregnancy before any additional injections, advice regarding additional contraception, and also for the timing of the next injection. She should be advised to have a pregnancy test conducted prior to administering her next Sayana Press injection either at home or at the clinic. The study centre must be informed if the subject has a positive at home pregnancy test and report to the clinic immediately. An Exposure During Pregnancy Form must be completed and submitted to Pfizer within 24 hours of awareness. The subject should also use a barrier method of contraception as instructed by the study investigator until she administers the next injection or, in cases when the subject decides to discontinue Sayana Press altogether, until the new contraceptive regimen is established.

Final Visit (Month 12 +/- 1 week) or Premature Discontinuation Visit

Subjects will return to the clinic for their final visit and the following procedures will be performed:

- AE assessment;
- Concomitant medications;
- , CCI

- Physical examination;
- Height and Weight;
- Vital signs (sitting blood pressure and heart rate);
- Urine pregnancy test;
- Plasma sample for analysis of MPA (at select sites);
- Drug accountability;
- End of study form procedures (administrative).

CCI	

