2.2. Endpoints

Primary Endpoint

The primary endpoint will be the proportion of all attempted home self-injections that were successfully performed by the study participant at home (ie, not in the clinic under direct HCP supervision) and on schedule (13 week interval +/- 1 week). If a subject decides to discontinue Sayana Press as her contraceptive method, and therefore does not attempt 1 or more injections, these scheduled injections would not be included in the denominator for the primary endpoint.

Secondary Endpoint

• Continuation rate for method at 1 year.

- Ease of self-injection, based on Question 10 of Subject Questionnaire (including any post-baseline self-injections that were performed under HCP supervision, which would not have been included in the primary analysis);
- Usefulness and type of reminder techniques used, based on Questions 5 and 6 of Subject Questionnaire;
- Proportion of attempted home self- injections where subject returned to clinic for the injection (to be administered by the a HCP or under supervision of one);
- Evaluate end of study plasma concentration of MPA;
- Reasons for electively discontinuing self-injection of Sayana Press (where the subject elects to continue to receive DMPA administered by a HCP at the clinic), based on Question 17 of Subject Questionnaire;
- Reasons for electively discontinuing Sayana Press altogether, based on Question 18 of Subject Questionnaire;
- Adverse Events (AEs), including unplanned pregnancy and persistent injection site reactions;
- Other information provided in Subject Questionnaire;
- HCP Questionnaire:
 - Percentage of suitable patients, based on Question 1;
 - Percentage of willing patients, based on Question 2;
 - Usefulness of training materials, based on Question 3;
 - Ease to teach a patient to self-inject, based on Question 4;
 - Overall experience/other information and input, based on Questions 5, 6, and 7

CCI		

Safety Analysis

Safety data, consisting of all adverse events, including unplanned pregnancies, persistent injection site reactions, SAEs, premature discontinuations, concomitant medications, vital signs, height and weight, and laboratory parameters, will be tabulated and listed according to Pfizer's standard reporting algorithms.

The study will be registered in the European Union (EU) in the EU Clinical Trials Register and in the United States in the ClinicalTrials.Gov registry, according to local requirements.

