3. STUDY DESIGN

This is an open-label, single-arm, 1-year study to assess home self-administration of Sayana Press in women who desire long-acting reversible contraception (LARC), are interested to attempt DMPA self-injection at home and are judged by their HCP to be good candidates for the self-injection option. Following training and a supervised initial self-injection at the clinic, study participants will self-inject Sayana Press in the home setting every 3 months (at Month 3, Month 6 and Month 9) and return for a final study visit at Month 12.

Approximately one hundred sixty (160) adult women subjects of reproductive age (18 to 45) will be enrolled at approximately 10 study centres in the UK (and other countries in Europe if required) with approximately 16 subjects per study centre, to ensure that at least 100 women will complete the study.

Participants will attend 2 or 3 study visits at the clinic: a Screening/Baseline Visit (or Screening and Baseline visits separately) and a Final Visit. At Months 3, 6 and 9, participants will be asked to contact the clinic by phone after performing each scheduled home self-injection in order to confirm the date of injection and to report any AEs, and/or injection difficulties or problems with the device. Should the injection site reactions occur, the centre staff will collect detailed information about these reactions. If at least 1 week has passed from the scheduled self-injection date and the clinic has not heard from the subject, the clinic staff will contact the subject to obtain the necessary information and provide appropriate instructions to the subject, depending on the circumstances. All AEs, including pregnancy and injection site reactions will be recorded on the AE Case Report Form (CRF) page. Reasons for self-injection failure will also be recorded in the CRF.

At the Month 12 Final Visit or Premature Discontinuation, subjects will be asked to complete the CCI

If a subject does not perform a scheduled self-injection at home for any reason, the subject should immediately contact the clinic to explain the reason why the injection was not performed. The HCP at the clinic must provide instructions to the subject regarding how the scheduled injection will be provided:

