7.1. Pregnancy Testing

Urine pregnancy test, with sensitivity of at least 25 mIU/mL, will be performed at Screening, before Sayana Press administration at the Baseline Visit, and at the Final Visit. A negative pregnancy result is required before the subject may receive the first Sayana Press injection. Pregnancy test will also be done in any instance when potential pregnancy is suspected, if the Sayana Press injection is not conducted per the required schedule and at the end of the study to confirm the subject has not become pregnant during the study. Pregnancy tests may also be repeated as per request of institutional review boards (IRBs)/ethics committees (ECs) or if required by local regulations. In the case of a positive confirmed pregnancy, the subject will be withdrawn from administration of the Sayana Press product and from the study.

If the subject fails to self-inject or report to clinic for an injection (supervised or administered by HCP) within the +/- 1 week treatment window, the subject should be advised to contact the clinic and speak to a healthcare professional regarding the need to exclude pregnancy before any additional injections, advice regarding additional contraception, and also for the timing of the next injection. She should be advised to have a pregnancy test conducted at home or at the clinic prior to administering her next Sayana Press injection. The study centre must be informed if the subject has a positive at home pregnancy test and report to the clinic immediately. An Exposure During Pregnancy Form must be completed and submitted to Pfizer within 24 hours of awareness. The subject should also use a barrier method of contraception as instructed by the study investigator until she administers the next injection or, in cases when the subject decides to discontinue Sayana Press altogether, until the new contraceptive regimen is established.

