9.2.1. Analysis of Primary Endpoint

The primary endpoint is the mean percent of home self-injections that were successfully administered. Each subject will have a maximum of 3 home self-injections, each of which will be defined as a success or failure. A success is defined as a home self-injection that was successfully performed by the study participant at home and on schedule (13 week interval +/-1 week). If the subject attempts but is unable to administer the self-injection at home and had it performed instead at the clinic, then that attempted self-injection would be classified as a failure. If a subject discontinues from the study prior to attempting all 3 home

self-injections, or chooses not to attempt an injection at home, but has it performed in the clinic, then only the injections that were attempted at home will be evaluated and included in the analysis; ie, all attempts are included in the denominator.

For each subject we will calculate:

Proportion of attempted self-injections successfully administered at home= (# of successful home self-injections) / (total # of home self-injection attempts)

These binary outcomes are correlated within the subject, and they will therefore be analyzed with a GEE model for clustered binomial data, using subject as the clustering variable. The GEE model for this single-group analysis will use the logit link and will contain an intercept term; the 95% confidence interval for the intercept will be transformed to a 95% confidence interval for the self-injection success rate.

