- If you believe for any reason that the full dose has not been given, speak to your healthcare provider about alternative methods of contraception until the next scheduled injection.
- Do not inject an additional dose.

After injection care:

• If you get any symptoms of allergic reaction (see leaflet Section 4 above) seek medical help immediately.

Monitor the appearance of the injection site until the next injection. If you notice any skin indentation or dimpling at the injection site, tell your healthcare provider.

Step 7: Disposing of the injector	
• Immediately dispose of the used injector into a suitable container in accordance with your local authority requirements or as you have been told by your healthcare provider.	
• The injector is for a single injection only and must not be re-used.	
Step 8	
• Record the date of your injection and should you wish to continue, calculate the date of your next scheduled injection of Sayana Press	

Retain this leaflet for your records.

CI

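### The final visit is fixed at Month 12 ± 1 week and not tied to the fourth injection, so in fully compliant women the closing assessments can fall 9 to 17 weeks after the last dose (11 to 15 if dates run from Day 1)

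*Protocol*

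**What the plan says.** Protocol section 3 plans three home injections after the supervised first one: "study participants will self-inject Sayana Press in the home setting every 3 months (at Month 3, Month 6 and Month 9". Section 6.2 gives the timing rule: "Study subjects will self-inject Sayana Press at home according to schedule (13 week interval +/- 1 week". The same rule defines success in section 9.2.1, where an injection counts if it was "successfully performed by the study participant at home and on schedule (13 week interval +/-1 week". Step 8 of the Instructions for Use (Protocol Appendix 2) tells the woman: "Record the date of your injection and should you wish to continue, calculate the date of your next scheduled injection of Sayana Press". Elsewhere (Schedule of Activities footnote g, sections 3 and 5.3.3) the window is one week either side of a scheduled date, with no statement of whether that date is counted from Day 1 or from the previous injection.

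The closing visit has its own rule, in section 6.2: "Final Visit (Month 12 +/- 1 week) or Premature Discontinuation Visit". It includes an AE assessment, a urine pregnancy test, which section 7.1 requires "at the end of the study to confirm the subject has not become pregnant during the study", and the physical examination that section 7.3 uses to look for lasting injection-site reactions. At select sites it also includes the plasma sample for a listed endpoint, "Evaluate end of study plasma concentration of MPA".

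Protocol section 8.2 has AEs recorded up to the subject's final visit. SAP section 6.7.1 closes the AE timeframe at the earlier of that visit and a point 14 weeks past the last injection.

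**The concern.** If each injection is timed from the one before, small deviations add up over three intervals, and a visit fixed near Month 12 does not move with them. The time from last dose to closing assessment then varies between women who all followed the plan.

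This matters in both directions. The planned phone calls follow the home injections, so after the Month 9 call the final visit is the only planned contact. A woman who ran late can be seen well before her last 12 to 14 week interval is over, and nothing planned observes the rest of it. A woman who ran early can be seen more than 14 weeks after her last dose. Findings that arise after week 14 are recorded under Protocol section 8.2 but lie outside the SAP timeframe. She is also beyond the interval after which sections 3 and 6.2, for a delayed injection, call for pregnancy to be excluded and contraceptive advice given, although no further study injection is planned for her. MPA values taken at such different times after dosing are hard to compare unless the interval is shown with them.

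**Working it through.** **Inputs.** Interval: 13 ± 1 weeks, so 12 to 14 (Protocol 6.2, 9.2.1). Home injections after baseline: 3 (section 3). Final visit: Month 12 ± 1 week (section 6.2). Assumption: Month 12 is 52 weeks from Day 1, which gives weeks 51 to 53. The documents state no required time from last dose to final visit, so there is no figure of that kind to reproduce. The nominal plan is coherent: 4 × 13 = 52 weeks, against 365.25 / 7 = 52.2 weeks in a year.

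**Outer limits, rolling reading** (each interval runs from the previous actual injection):
- Last injection: 3 × 12 = 36 to 3 × 14 = 42 weeks.
- Gap = visit − last injection: 51 − 42 = 9 to 53 − 36 = 17 weeks (63 to 119 days).
- With the visit exactly at week 52: 52 − 42 = 10 to 52 − 36 = 16 weeks.
- With Month 12 taken as 365 days: 9.1 to 17.1 weeks.

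**Outer limits, Day 1 reading** (due dates fixed in advance):
- Last injection: 39 ± 1, so 38 to 40 weeks.
- Gap: 51 − 40 = 11 to 53 − 38 = 15 weeks.

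Both readings pass 14 weeks at the upper end and fall short of 12 at the lower end.

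**How often, under assumed deviations.** The gap equals 13 weeks plus a sum of independent deviations: four on the rolling reading (three intervals and the visit), two on the Day 1 reading (the last injection and the visit). The documents give no distribution, so these are illustrations.

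*Uniform on ± 1 week:*
- Rolling: P(gap > 14 weeks) = (1.5⁴ − 4 × 0.5⁴) / 24 = (5.0625 − 0.25) / 24 = 0.2005, and by symmetry the same below 12 weeks. A simulation of 1,000,000 women gave 0.200 on each side, with the central 95% at about 10.8 to 15.2 weeks.
- Day 1: 0.5² / 2 = 0.125 on each side. The simulation gave 0.125, with the central 95% at about 11.4 to 14.6 weeks.

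*Tighter behaviour, rolling reading, normal deviations centred on zero:*
- SD 2 days each: gap SD = 2 × √4 = 4 days; 7 / 4 = 1.75; about 4% on each side.
- SD 2.5 days each: gap SD = 5 days; 7 / 5 = 1.4; about 8% on each side.

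**AE timeframes side by side.** For a visit at 14 weeks or earlier, the protocol and the SAP end AE collection at the same point, the visit. For a visit at week 17, the protocol runs to week 17 and the SAP stops at week 14, a difference of 17 − 14 = 3 weeks.

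**The case against.** A visit fixed near one year is defensible in a study meant to mirror practice with a one-year continuation endpoint. The 9 and 17 week limits need all three intervals and the visit to deviate fully in the adverse direction, and the typical gap stays near 13 weeks. The rolling anchor is inferred: the leaflet implies it but does not say from which date to calculate. The percentages depend on the assumed spread. All of this stands, and it is why the point concerns what can happen. It does not remove the problem, because even the Day 1 reading gives 11 to 15 weeks.

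Three stronger inferences are tempting, and the documents do not support them.

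- *Late pregnancies and reactions are missed.* Protocol 8.1 provides for follow-up of AEs, 8.2 takes later serious events that the investigator learns of, and 8.10 covers pregnancy found after stopping. What is lacking is a planned contact, so events may go unobserved.
- *A conception after week 14 would be counted as lack of efficacy.* SAP 6.7.1 ends the timeframe at 14 weeks, so an event arising later falls outside it. Protocol 1.2 also describes return to fertility as generally taking six months or more, so such conceptions should be rare.
- *The MPA endpoint is invalid.* The protocol claims an end-of-study concentration, not an end-of-interval one. Sampling is at select sites only, and the analysis text may be among the redacted sections, so reporting by time since dose may already be planned.

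**Conclusion.** The point holds as a gap in the design of the closing visit. Nothing visible ties that visit to the fourth injection. In fully compliant women the time from last dose to final visit can range over 9 to 17 weeks (rolling) or 11 to 15 weeks (Day 1), taking Month 12 as 52 weeks from Day 1. The share outside 12 to 14 weeks is about 40% in total (rolling) or 25% (Day 1) under uniform deviations. On the rolling reading it is about 8% in total if each deviation has an SD of 2 days. Premature discontinuation visits and out-of-window injections are not covered by these figures.

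The consequences are uneven closing observation for pregnancy, injection sites and AEs, a mismatch between Protocol 8.2 and SAP 6.7.1 for visits after week 14, and MPA values that need their sampling interval to be interpretable. The primary endpoint does not use the final visit and is unaffected.

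**What to change.** 1. In Protocol 6.2, the Schedule of Activities and SAP 2.2, define the final visit for women who receive the fourth injection as 13 weeks ± 1 week after its recorded date, keeping Month 12 as the nominal label. The gap is then 12 to 14 weeks whatever drift came before.
2. State whether the scheduled injection date runs from Day 1 or from the previous injection.
3. Derive days from last injection to final visit, and present MPA results and any pregnancy with that interval.
4. Reconcile Protocol 6.2 (visit window), Protocol 8.2 (AE recording) and SAP 6.7.1 (14-week limit). The passages on what follows once the injection window has passed must also be reconciled with the visit timing for any woman still seen after week 14.

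**Cost.** Protocol and SAP wording and one derived variable. Injection dates are already collected, and no visit or procedure is added. The visit would float: on the rolling reading from 36 + 12 = 48 to 42 + 14 = 56 weeks in compliant women, and later after a delayed dose. One-year continuation would then be read at a slightly variable time. This matters little, because Protocol 9.2.2 and SAP 6.2 define completion by four injections, a follow-up visit and no recorded discontinuation, not by an exact week.
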